## 1.0 Objectives/Specific Aims

Each year, an estimated 34,000 spinal cord stimulation (SCS) surgeries are performed worldwide for treatment of debilitating chronic low back and leg pain (CLBLP). Although the commercial application of SCS to treat CLBLP was approved by the FDA in 1989, only in the past decade have significant advancements in stimulator technology been introduced. For instance, traditional SCS devices achieved reduction in pain using a type of stimulation known as low-frequency tonic stimulation (LFTS, below 100 Hz), which was dependent on induction of paresthesias (i.e., a tingling sensation) over the areas of pain perception. However, we now know that LFTS compromises sensory information flowing back to the spinal cord, which can be important in other spinal cord functions such as proprioception and movement. In contrast, recent innovations in stimulator technology now provide the capability to apply stimulation frequencies up to 10,000 Hz along with complex waveform patterns – known as high frequency burst stimulation or HFBS – that can mitigate pain perception without the induction of paresthesias and the negative consequences on proprioception and movement. We propose to study the effects of these recently introduced features in SCS technology on motor and sensory spinal thresholds, proprioception and movement in subjects with CLBLP.

The spinal cord relies on input from the motor cortex as well as sensory information from the extremities to carry out specific actions. For example, recent evidence suggests that preservation of temporally specific proprioceptive information via dorsal column primary afferent fibers is critical for motor behaviors such as ambulation. Since the spinal cord is exposed during the placement of the SCS device, information about a subject's motor and sensory spinal pathways can be easily obtained during the regular course of the procedure and compared to proprioceptive and motor responses once the subject is awake and moving with the device turned on. Our lab specializes in electrophysiological recordings in subjects undergoing spinal cord stimulator (SCS) implantation for CLBLP, while MUSC's Locomotion Laboratory specializes in quantifying proprioception and movement in human subjects. In this proposal, we will apply these techniques to subjects with CLBLP to determine effects of spinal neuromodulation on motor and sensory thresholds, proprioception, and kinematics. Our plan includes the following specific aims:

**Aim 1. Compare the effects of LFTS and HFBS on motor and sensory thresholds intraoperatively.** Question: Do HFBS waveform patterns modulate motor and sensory thresholds to allow more information to reach the spinal cord? In this aim, we will measure sensory and motor spinal thresholds in subjects undergoing SCS implantation during stimulation of epidural paddle contacts. *We hypothesize that HFBS will reduce motor and sensory thresholds relative to LFTS during epidural paddle activation.*

**Aim 2. Determine the effect of HFBS on proprioceptive afferent signaling from lower extremity muscle groups.** Question: Does HFBS, when compared to traditional LFTS, allow for increased spatial limb awareness during passive motion? In this aim, postoperative subjects from SA1 will undergo isokinetic passive proprioceptive testing before, during and after spinal cord stimulation with HFBS and LFTS parameters targeting musculature surrounding the knee. *We hypothesize that subjects will have increased awareness of the lower limb in space through passive movement during optimal HFBS compared to optimal LFTS parameters.*

**Aim 3. Determine the effect of HFBS on lower extremity musculature during gait.** Question: Does HFBS, when compared to LFTS, differentially affect muscle synergy patterns during gait? In this aim, subjects from SA1 and SA2 will perform treadmill walking before, during and after SCS stimulation. Subjects will be monitored with surface EMG and 3-D kinematic tracking software to quantify any changes in walking pattern. *We hypothesize that subjects will have increased EMG module complexity during gait while experiencing optimal HFBS compared to optimal LFTS or no stimulation.*

Date: 8/1/19

Version: 01

## 2.0 Background

### Significance

SCS is currently used to treat chronic neuropathic pain that may arise from spinal injury, disease, and/or previous spinal surgery, for example, in cases of post-laminectomy syndrome, the most common indication for SCS. SCS surgery represents 70% of all neuromodulation cases in the United States and is expected to grow as the intervention shows continued promise to successfully treat neuropathic pain from these and many other etiologies. With the introduction of new charging capacities, stimulation frequencies and waveform patterns, questions about potentially new mechanisms of pain reduction as well as effects on other spinal cord functions, such as movement and balance, have gained urgency.

SCS was originally based on a concept known as the gate control theory of pain. Gate control theory postulates that central regulation of pain involves nonnociceptive fibers (large A $\beta$  fibers in the dorsal column medial lemniscal pathway) that inhibit nociceptive fibers (A $\delta$  and C fibers in the spinothalamic pathway) and thus reduce both pain transmission in the spinal cord as well as perception by higher brain centers. The SCS procedure involves placement of epidural electrodes that when activated recruit lower threshold A $\beta$  fibers that produce a paresthetic sensation along the region of pain. The antidromic projections to dorsal horn interneurons influence two additional downstream targets: fibers that further inhibit pain transmission and ventral motor neuron pools that target specific myotomes.

In 2009 Harkema et al investigated the motor effects from LFTS at intensities strong enough to elicit paresthesias, ranging from 5-60 Hz (frequency), 210 to 450  $\mu$ s (pulse width) and amplitude ranging from 0.1 to 8.0 V. Using these parameters, LFTS was found to elicit lower extremity muscle activity including co-activation during standing, rhythmic activation during stepping, and mechanically appropriate activation of agonist lower extremity muscles during weight shift in a subject with spinal cord injury. Additionally, Gill et al introduced the application of multiple independent current control (MICC) which allows for different stimulation parameters on the paddle to be delivered in tandem, innervating spatially distinct regions of the spinal cord. The MICC programs supported bilateral tasks, suggesting that complex charge delivery via MICC can enable independent modulation of both spinal sensory and motor neuron pools.

The ability to program customized HFBS patterns may help to address another important factor in potentially expanding the use of SCS to other indications, including movement: preservation of proprioception. The amount of compromised afferent information during traditional spinal cord stimulation via LFTS is dependent upon the quantity of dorsal column primary afferents recruited and is proportional to increases in current and pulse width. Traditional stimulation parameters (15Hz-100Hz, 210 $\mu$ s-450 $\mu$ s, 4.5mA-9.0mA) were found to cause decreased interneuron modulation of inhibitory/excitatory interneurons from antidromic collision when amplitudes are high enough to innervate their homonymous motor neuron pool to activation threshold. However, high frequency burst stimulation (HFBS) at 600Hz was found to illicit motor neuron activation with a 39.8% reduction in current amplitude and 15% recruitment of modeled homonymous afferents, as opposed to 45% recruitment utilizing LFTS to elicit similar motor neuron activation.

## 3.0 Intervention to be studied

### Overview

This study will perform the following research-specific procedures:

- 1) Determination of eligibility through medical chart review
- 2) Recording and stimulation of spinal potentials during insertion of epidural spinal stimulator paddle
- 3) Proprioception testing
- 4) Body weight support and treadmill (BWST) testing

## Definitions and nomenclature

Spinal cord stimulation (SCS) will be performed using a 32-electrode paddle array (Boston Scientific, Marlborough, MA) (Figure 1) implanted in the dorsal epidural space along the thoracolumbar region of the spinal cord. The array will be powered by a multiple independent current-controlled (MICC) implantable pulse generator (IPG) connected to the paddle per standard of care procedures for SCS implantation. In addition, as per standard of care, motor evoked potential (MEP), somatosensory evoked potential (SSEP) and electromyography (EMG) will be performed via the IOMAX intraoperative neuromonitoring system (Cadwell, Kennewick, WA) and LR10 (Tucker Davis Technologies, Alachua, FL) recording device. **The SCS system will be placed for clinical purposes, i.e., treatment of chronic pain, however, we will collect data at various points during the placement. The study procedures will add 15 minutes to the surgery.** MUSC's Locomotion Rehabilitation Laboratory – located at the College of Health Professions Building C - houses a Biodex Pro System 4 isokinetic/isometric dynamometer (Biodex Medical Systems, Shirley, NY). The Biodex will standardize application of passive isokinetic knee flexion/extension trials to each blinded subject for proprioceptive investigations, which will be referred to as threshold to detect passive movement (TTDPM) throughout the rest of this document. Finally, MUSC's Locomotor Energetics and Assessment Laboratory – also located at the College of Health Professions Building C – houses a dual belt Instrumental Treadmill (Bertec, Scotland, U.K.) that is coplanar with the floor and will be used during all walking events. The laboratory also has a 12-camera motion capture system (PhaseSpace, San Leandro, CA) that utilizes active infrared LED tracers to track kinematic positioning data and will be used during all walking events. Another tool offered by the lab is a 16-channel EMG system (Motion Labs, Baton Rouge, LA, model MA300-XVI) which utilizes surface electrodes to detect target muscle activity and will also be used during all walking events. In all, we expect total duration of the study to be approximately 30 days.

[figure not shown]

Figure 1: Boston Scientific CoverEdge™ 32 Surgical Lead (left) and fluoroscopic image of the stimulator array after implantation along the dorsal epidural space (right).

## Device use

The epidural stimulator paddle (Boston Scientific, Marlborough, MA, model 4x8 CoverEdge™ 32) and IPG (Boston Scientific, Marlborough, MA, model Spectra WaveWriter™) are FDA-approved, commercially available devices designed to treat chronic pain of the back and lower extremities and will be used for their intended clinical purpose – electrical stimulation of dorsal column fibers to mitigate pain perception. The research use of this device, which will add approximately 15 minutes to the surgery, involves recording/stimulating from the device during the standard of care intraoperative neuromonitoring protocol. Regardless of study participation, the stimulator paddle and IPG will be implanted according to standard of care for the pre-planned SCS surgery. The IOMAX intraoperative neuromonitoring system (Cadwell, Kennewick, WA), equipment owned by MUSC and operated by MUSC neurophysiology staff, is a commercially available device used during standard of care spinal surgical procedures, such as SCS implantation. Regardless of study participation, intraoperative neuromonitoring via IOMAX will take place according to standard of care for the pre-planned SCS surgery. The following devices are used for research purposes only. The LR10 is a physiological signal amplifier and analog to digital converter that will be used to record from the stimulator paddle during standard of care neuromonitoring protocols. The Biodex Pro System 4 (Biodex Medical Systems, Shirley, NY), used regularly by physical rehabilitation researchers here at MUSC, is a commercially available device that will be used solely as a research tool to deliver passive isokinetic knee flexion/extension during the TTDPM. The Instrumental Treadmill (Bertec, Scotland, U.K), GAITRite mat (CIR Systems, Franklin, NJ), motion capture system (PhaseSpace, San Leandro, CA), and MA300 EMG system (Motion Labs, Baton Rouge, LA) are all commercially available devices that are used by MUSC researchers at the College of Health Professions to perform extensive gait analysis in subjects with various neurological deficits. Gait analysis is being performed

Date: 8/1/19

Version: 01

for research purposes only, and is not standard of care for patients receiving SCS surgery. All medical devices are to be used as they are FDA approved and marketed.

#### **4.0 Inclusion and Exclusion Criteria / Study Population.**

All diagnostic procedures will have taken place prior to recruitment as part of the routine diagnosis and care of patients with chronic pain. It is standard of care to require failure of conservative therapy, e.g., 6 weeks of physical therapy and/or 1 or more epidural steroid injections, and SCS temporary trial by a board-certified **pain management specialist** in addition to neuropsychological testing by a board-certified neuropsychologist prior to being considered for permanent SCS implantation.

Eligibility for this study will be based on the following inclusion/exclusion criteria:

##### **Research Inclusion Criteria**

- Subjects diagnosed with CLBLP by a **pain specialist** with a documented referral for evaluation of SCS surgery
- Subjects with the ability to walk
- Age 18-80

##### **Research Exclusion Criteria**

- Subjects with the inability to consent for themselves.
- Prior history of spinal neoplasm, infection, arteriovenous malformation and/or radiation to the spine

The rationale for these research related criteria are as follows: subjects with prior history of tumor, infection, arteriovenous malformation and/or radiation of the tissues surrounding the epidural space may result in formation of scar tissue which directly alters the resistance of the tissue to passing electrical current, potentially confounding study data. None of the research exclusion criteria would exclude a patient from undergoing SCS surgery for non-research purposes, therefore the exclusion criteria apply only to the research being performed for this protocol.

#### **5.0 Number of Subjects**

We propose to study 5 individuals with CLBLP. A prior study conducted by Formento et al, 2018 using SCS and proprioceptive testing published a standard error and 95% confidence interval using successful and unsuccessful SCS trial attempts ( $p < 0.05$  among LFTS parameters and no stimulation, with a minimum of 10 trials per stimulation setting). Based on this, we expect that our small population will exhibit similar variance. The subject sample size is in direct comparison to sample sizes of previous proof of concept studies regarding SCS for spinal cord physiology biomarker sampling. The research team plans to use a two-way repeated measures ANOVA model in order to investigate the varying differences in stimulation type and kinematic parameters. A Post hoc comparison will be made using a Tukey adjustment.

#### **6.0 Setting**

The data pertaining to Aim 1 for this study will be recorded in the operating room at MUSC Main Hospital. Data collected during Aims 2 and 3 will be recorded in the Locomotor Rehabilitation Laboratory and the Locomotor Energetics and Assessment Laboratory respectively, which are both located in the College of Health Professions Building C at MUSC. Coded and identifiable data will be stored electronically on a secure server in separate folders. Signed consent forms will be located in a locked cabinet in a locked laboratory in the Clinical Sciences Building at MUSC. In all, we expect total duration of the study to be approximately 30 days for each subject.

#### **7.0 Recruitment Methods**

Date: 8/1/19

Version: 01

During the subject's preoperative clinic visit, the PI will ask the potential participant if they would like to learn more about the study. If so, the PI will introduce the study and ask if he can answer any further questions about the study before inviting in the PI's physician assistant (listed as a study team member). The PI will then leave the room and the PI's physician assistant will review a prescreening checklist to determine whether subjects may be eligible for the study (no information obtained during the prescreening will be documented as research data). For the screening, potential participants will be asked to confirm that they are between the ages of 18 and 80, that they have been previously diagnosed with CLBLP by a pain specialist, and whether they have any prior history of spinal neoplasm, infection, arteriovenous malformation and/or radiation to the spine. If potential participants answer no to either of the first two questions or yes to either of the remaining questions, they will be considered ineligible for the study. Otherwise, the PI's physician assistant will review the informed consent form (ICF) with the potential participant and then leave the room in order to give the potential participant sufficient time to read the ICF.

Next, the PI's physician assistant will conduct a brief medical chart review using Epic to confirm that the patient's age is between 18 and 80 and that the patient has a documented referral from a pain specialist to undergo evaluation by the PI to undergo SCS surgery. The Epic 'Medical History' tab will also be checked to rule out prior history of spinal neoplasm, infection, arteriovenous malformation and/or radiation to the spine.

Careful attention will be placed on good communication. It will be emphasized that participation in the study is not necessary for standard of care medical treatment for their condition. It will also be emphasized that the subject can withdraw from the study at any time.

## **8.0 Consent Process**

Once the potential participant has been given an opportunity to review the consent form in detail, the PI's physician assistant will re-enter the room and go over the sections of the consent with the participant. She will answer any questions the potential participant may have. The voluntary nature of the study will again be emphasized. It will also be emphasized that the potential participant may exercise their right to take the consent form home to discuss with family and friends prior to signing. For potential subjects that provide consent to the research study during their clinic visit, a copy of the signed and dated ICF/HIPAA authorization form will be provided to them before leaving the clinic. Original forms will be placed in a locked cabinet in a locked laboratory in the Clinical Sciences Building at MUSC. On the morning of surgery, IRB-approved study personnel will once again review the study procedures and study consent documents – emphasizing the voluntary nature of the study and the ability of the subject to withdraw at any time. Subjects who did not sign the ICF/HIPAA authorization form during their clinic visit and who still wish to participate in the study will be able to sign the forms on the morning of surgery, at which time a copy of the signed and dated forms will be provided to them.

## **9.0 Study Design / Methods**

### **Step 1: Recording and stimulation of spinal potentials during insertion of epidural spinal stimulator paddle**

On the day of the surgery, subjects will first be placed under general anesthesia for the procedure. Next, after positioning the subject on the operating room table, subdermal MEP, SSEP and EMG needle electrodes will be placed throughout the body by the neurophysiology team as determined by standard of care guidelines. Once the epidural paddle is placed by the surgeon, study procedures will begin by (#1) connecting the terminals of the paddle to the LR10 (Tucker Davis Technologies, Alachua, FL) for amplification, filtering and recording of electrophysiological signals. Using this recording setup, (#2) MEP and SSEP protocols will be performed to determine motor and sensory thresholds, respectively. Next, the surgical procedure will resume and after the IPG has been placed, study procedures will begin again and include (#3) activation of both low-frequency tonic stimulation (LFTS) and high-frequency burst stimulation (HFBS) patterns from the inserted paddle while recording EMG signals. The surgical procedure being performed (SCS paddle and IPG implantation) for

Date: 8/1/19

Version: 01

clinical purposes will not deviate in any way from standard of care. The recording and stimulation study procedures will occur using equipment already present in the operating room used to test the SCS system as per standard of care in addition to the LR10 (Tucker Davis Technologies, Alachua, FL) signal recording machine. All devices will be used for their FDA-approved intended use. Our study procedures are expected to add approximately 15 minutes to the SCS procedure and will be paid for by internal funds. The standard of care versus the research procedures are diagramed below:

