### Standard of care procedures

Subject is placed under general anesthesia and positioned face down. The neurophysiology team places subdermal needles for MEP, SSEP and EMG measurements and connects the wires to the **IOMAX intraoperative neuromonitoring system** (owned and paid for by MUSC). Skin incision is made. The SCS paddle is placed into initial position.

The neurophysiology team then performs MEP and SSEP measurements. The surgeon makes small adjustments to the position of the paddle based on this information.

Once the SCS paddle is in its final position, the SCS paddle terminals are disconnected from the LR10 machine and reconnected to a **Boston Scientific external stimulator** (owned and paid for by Boston Scientific – leaves the OR with Boston Scientific representative). The stimulator tests the impedance of each contact.

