### Research procedures

Once the SCS paddle is in initial position, the research team connects the SCS paddle terminals to the **LR10 machine** (owned and paid for by the [name] lab, takes less than 1 minute).

The research team saves data from the SCS paddle as the MEP and SSEP measurements are performed (takes 0 minutes).

Once the impedances are confirmed, the external stimulator is used to test each contact on the paddle and compare low- and high-frequency stimulation patterns as prescribed by the study protocol (takes approximately 15 minutes).

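### Step 1 describes no sensory threshold measurement under LFTS or HFBS, and no rule for a motor threshold under either, although Aim 1 compares both thresholds between the two patterns

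*Combined protocol and SAP*

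**What the plan says.** Section 1.0, Aim 1, commits to a measurement made while the paddle is stimulating: "we will measure sensory and motor spinal thresholds in subjects undergoing SCS implantation during stimulation of epidural paddle contacts". The hypothesis is that "HFBS will reduce motor and sensory thresholds relative to LFTS during epidural paddle activation".

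Section 9.0, Step 1, sets out the intraoperative sequence. At item #1 the paddle is connected to the LR10 for recording. At item #2, "MEP and SSEP protocols will be performed to determine motor and sensory thresholds, respectively". Surgery then resumes. Once the pulse generator is in, both patterns are switched on, and the readout is given in these terms: "high-frequency burst stimulation (HFBS) patterns from the inserted paddle while recording EMG signals".

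The two lists that follow keep the same order. Under Standard of care procedures, with the paddle in its initial position, "The neurophysiology team then performs MEP and SSEP measurements". The paddle is later unplugged from the LR10 and joined to the external stimulator. Under Research procedures, "Once the impedances are confirmed, the external stimulator is used to test each contact on the paddle and compare low- and high-frequency stimulation patterns". For the details that list refers back to the protocol, and it allots about a quarter of an hour.

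**The concern.** The Aim 1 hypothesis is a within-subject contrast between two stimulation patterns, so it needs a threshold under LFTS and a threshold under HFBS, for each modality. Step 1 uses SSEP for the sensory threshold, but places it before either pattern has been delivered. That value belongs to neither arm of the contrast. At the stage when the patterns are on, no sensory readout is named.

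The motor side has a related weakness. Step 1 uses MEP for the motor threshold, also at item #2. EMG is recorded under both patterns at item #3, but nothing says how an EMG trace becomes a threshold.

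This matters because each subject has one operation. A sensory measurement not taken in theatre cannot be recovered at the visit about 30 days later, when the subject is awake. The hypothesis would then be reported with its sensory half unsupported, or with a measure chosen after the fact. Aims 2 and 3 use other measurements and are not touched.

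**Working it through.** The plan gives no figure to reproduce here. The check sets what Aim 1 needs beside what each stage of Step 1 provides.

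| Stage (section 9.0, Step 1) | Paddle role | Pattern on | Readout named | Sensory threshold | Motor threshold |
|---|---|---|---|---|---|
| Item #2 | Recording, via LR10 | None | MEP, SSEP | Yes (SSEP) | Yes (MEP) |
| Item #3, LFTS | Stimulating | LFTS | EMG | None described | EMG, no threshold rule |
| Item #3, HFBS | Stimulating | HFBS | EMG | None described | EMG, no threshold rule |

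**Sensory count.** Values needed per subject: 2 (one per pattern). Values described: 0. Over the 5 subjects in section 5.0, 5 × 2 = 10 values are needed and 0 are described, so 0 of 5 paired HFBS-minus-LFTS differences follow from the text. This count restates the gap in the procedure; it is not an estimate of data loss.

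**Motor count.** A readout exists under both patterns (2 of 2). A rule turning it into a threshold exists under neither (0 of 2).

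**Does the order depend on which account is followed?** The Step 1 narrative puts the patterns after placement of the pulse generator. The Research procedures list puts them after the impedance check, using the external stimulator. On either account they come after the SSEP measurements.

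**Could another section supply the missing value?**
- Device use (section 3.0) describes the research as recording and stimulating during routine neuromonitoring, without naming a sensory measure under a pattern.
- Section 10.0 lists signals from SSEP electrodes among the data, without saying when they are taken.
- Step 2 maps muscle activation about 30 days later, which is not a sensory threshold and not intraoperative.
- Section 5.0 gives one model, for stimulation type and kinematic measures. It omits thresholds of both kinds, so it neither fills the gap nor shows a gap specific to the sensory side.

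**Time available.** Research procedures allots about 15 minutes, 15 × 60 = 900 s. With 32 contacts (section 3.0) and 2 patterns there are 64 combinations, and 900/64 ≈ 14 s each, assuming an even split with no switching time. No SSEP time is budgeted. The documents do not say how long an SSEP threshold run takes, or whether EMG could be recorded at the same time, so the number of contacts displaced cannot be calculated.

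**The case against.** The strongest reply is that the protocol must be read as a whole. Aim 1 itself says sensory thresholds are measured during paddle stimulation. Item #3 is introduced with a verb that does not close the list, so SSEP is not excluded. SSEP electrodes are in place, their signals are listed in section 10.0, and Research procedures refers back to the study protocol, which contains Aim 1. References 12 and 13, cited on the item #3 sentence, could not be read and might describe more.

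Much of this stands. A reader might infer that the sensory comparison is impossible under this protocol. The documents do not support that: they leave SSEP during stimulation open, and the defect is that Step 1 does not provide for it. What does not stand is the idea that Aim 1 cures the problem. Aim 1 states the goal, and the methods section, which has to carry it out, places SSEP elsewhere and names a different readout when the patterns are on. The references are attached to the EMG sentence, and the protocol does not say that it adopts an SSEP threshold procedure from them.

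A second reply is that five-subject proof-of-concept work can leave such detail to the laboratory. That is fair for settings and run times. It is less fair for the measurement on which half of a stated hypothesis rests.

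**Conclusion.** The point holds as a mismatch between Aim 1 and the Step 1 procedures. Followed as written, Step 1 yields no sensory threshold under LFTS or HFBS (0 of 2 values per subject), and a motor readout without a threshold rule. It should be corrected before enrollment.

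Two further inferences are tempting and should be resisted. One is that the motor half of Aim 1 is sound: it is better placed than the sensory half, but Step 1 ties the motor threshold to MEP at item #2, so an EMG threshold at item #3 still has to be defined. The other is that a definite number of contacts would be lost, or that a definite run time decides feasibility: both would rest on an SSEP run time that the documents do not give. Time is also not the only question. Nothing in the documents shows that an SSEP threshold can be read while the paddle is stimulating, and section 2.0 itself describes antidromic collision with traditional stimulation parameters.

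The conclusion assumes that item #3 is carried out as described, with EMG as its readout, and that the unread references add no SSEP procedure. Confidence is moderate for those reasons.

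**What to change.** In item #3 of Step 1, and in the matching entry under Research procedures:

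- State that SSEP thresholds are determined under LFTS and under HFBS, using the IOMAX electrodes already in place, at a contact setting fixed in advance.
- Name the within-subject HFBS-minus-LFTS difference in SSEP threshold as the Aim 1 sensory comparison.
- Define the motor threshold at item #3, for example as the lowest amplitude that gives an EMG response.
- Before enrollment, have the neurophysiology team confirm that SSEP thresholds can be obtained during stimulation, in both time and signal quality. If they cannot, restrict the Aim 1 hypothesis and conclusion to motor thresholds.

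The monitoring board's review of the protocol before enrollment (section 11.0) is a natural point to settle this.

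The cost is modest. No new equipment is needed. Some of the roughly 15-minute window goes to SSEP, so fewer contacts may be tested with EMG; how many cannot be derived from the documents. The Step 2 mapping tests every contact later, but in awake subjects, so it only partly makes up for this. A single preset setting also tests the sensory question more narrowly than Aim 1's wording about paddle contacts suggests. The fallback is a text change that gives up the sensory half of Aim 1.
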